4.4 Phase 2: Technology Evaluation and Comparative Assessment

Objective 2: Evaluate the effectiveness of the VR simulation in preparing patients for MRI, and compare to other modalities (i.e. booklet, simulation with CLS).

Protocol for Evaluating the Virtual Reality MRI Simulator

The goal of Phase 2 is to evaluate the effectiveness of the intervention on the basis of its ability to prepare patients and families for the MRI procedure. To do so, this phase will establish evidence to investigate whether the VR intervention can be implemented to reduce anxiety and efficiently prepare children for non-sedated MRI scans. Our needs assessment has identified that new accessible behavioral interventions are both needed and desired to alleviate the anxiety and lack of preparation necessitating sedation during medical imaging with children who live afar, who are not mobile, and who need extra practice. Virtual preparation is a promising practice that has been found to be safe, feasible, and acceptable in multiple clinical care settings.^{12,13,16,20,25}

The project evaluation plan consists of comparing the current modes of delivery through an objective assessment of movement and inquiry into the acceptability and utility of the intervention components, including potential barriers to adherence or behavioral change that could have unintended consequences. This information will help to generate knowledge that can be used to refine the current prototype and support future innovation in this domain at BCCH (Phase 4, not included in this proposal).

[figure not shown]

Figure 2. Evaluation design.

The recruitment strategy has been informed by the literature on recruitment in pediatric research settings.²⁶⁻²⁸ The design and expansion of the recruitment strategy has enacted as a response to the low enrollment rate arising from traditional strategies (posters that we had initially proposed). Participants will be recruited through:

- **Advertisements, flyers, internet postings and/or social media through the Digital Lab website (www.bcchdigital.ca), the BCCHRI website, social media, and through hospital and community recruitment boards.** Community focused recruitment will include flyers and posters distributed to various public places such as local supermarkets, children's stores, playgrounds, clinics, and coffee shops with applicable advertisement boards for community postings. The use of Facebook Ads has been emerging in the literature as a recruitment strategy. A typical ad will be comprised of a succinct description about the research with a hyperlink that directs the Facebook user to the recruitment poster with more information about the study's eligibility criteria, compensation, and enrolment instructions.²⁹ Our ad was designed following the recommendations of Wozney et al. (2019) who recommend in video format. Our content was selected to appeal to caregivers of children between 4 to 13 years. Audience targeted fields in the Facebook ad manager will be selected to show ads to users with specific interests and demographics (e.g. children between the ages of 4 and 13, located in

Vancouver, BC). Facebook analytics will be used to track actions related to the ads.

- **Direct recruitment of potential study participants through clinical staff at the Hospital (BCCH) talking with their own or clinic patients about the study and/or contact between the study team and the potential participants on the phone or via email.** Any initial contact made by our study will be by someone who is thoroughly knowledgeable about the study, able to answer questions, and trained in the voluntary nature of the research participation.

Parents/participants will be invited to initiate participation in the evaluation by emailing or calling the Research Manager ([contact]; [contact] [name]). The study parameters will be reviewed with the prospective participants, and informed consent will be emailed to the participant. Verbal consent (provided over the phone or through email) will be obtained to initial allocation, and written informed consent (parent or guardian) and assent (participant over 7 years) will follow in-person. Participants will be reimbursed for parking and provided snacks and refreshments during inactive segments of the evaluation process. A \$20 remuneration will be provided to each participant for their time volunteering in the study components.

A minimum of 93 participants (31 participants per group) aged 4-to-13 will be recruited through convenience sampling, consented, and randomized by staff to one-of-three preparation programs (VR, mock MRI, or booklet). Details of the comparison groups are outlined in **Table 4**. Given the restricted availability of the simulator, child life specialists, and the availability of participants, we are unable to fully randomly allocate participants. As such, participants will be randomly assigned to the intervention options available according to their individual availability (using Research Randomizer <https://www.randomizer.org/>). For example, if a participant is available on a Thursday that virtual reality and booklet are available, they will be randomly allocated to one of these interventions.

This phase will have open recruitment to all children and adolescents interested in participating, such that participants may not be BCCH patients scheduled for an MRI. This recruitment strategy was selected due to the resource constraints associated with limiting the evaluation group to MRI patients only.

Table 4. Details of the comparison groups.

	VR Simulation	MRI Preparation Booklet	Mock MRI
Facilitator	Research Assistant	Research Assistant	Child Life Specialist
Location	BCCH	BCCH	Simulation Room
Content	Refer to The Virtual Reality Simulation	Refer to MRI Preparation Book	Individualized intervention in physical simulator.

The different interventions will be held in separate private rooms located in BCCH, such that the VR and booklet groups will not have prior exposure to the imaging centre or the simulation room in advance of their assessment. This is to simulate our intended delivery in hospital, medical office, or clinic settings but minimize alternative explanations associated with testing in the simulation room where assessments will take place (previously described in **Table 3**).

Data will be collected throughout the implementation process (**Figure 3**). The predictive variables (demographics and relevant history, and delivery type) will be captured at the start of the session. The primary outcome variable is likelihood of success (pass/fail) of the MRI simulation, and will be measured at the end of the assessment. Anxiety will also be measured at three time points. Usability testing will be conducted throughout to capture possible quality improvements and amendments to each of the program delivery modes.

Inclusion/Exclusion Criteria

Participants must be between the ages of 4-to-13 years to be included in the evaluation.

The following exclusion criteria, which have been noted in previous studies conducted using virtual reality programs, will be adopted for this project:

- mental disability (content not appropriate)
- significant visual and auditory impairment (this program focuses on auditory and visual cues)
- inability to speak or understand English (content and study staff are English speaking)
- history of seizures or epilepsy (triggered by virtual reality)
- facial or head wounds (cannot wear the virtual reality headset)

Implementation Plan

[figure not shown]

Figure 3. Implementation process.

The testing phase of the implementation process, depicted in Figure 3 will be completed over two hours, and will involve the following steps:

- 1) Participants and parents/guardians are greeted by staff and enter the intervention room.
- 2) Staff will obtain written consent from parents and verbal assent from children (5 minutes).
- 3) Participants will complete the Venham Picture Test (VPT) with staff (pre-test). In parallel, parents will complete the Short STAI on the iPad. (5 minutes)
- 4) Staff will reveal the allocated delivery mode (VR, mock MRI, or booklet) to the participant and explain the procedure.
- 5) Staff will ask participants to indicate on the Smileyometer how good they think the intervention is going to be.^{30,31} This will give a measure of expectation that can indicate whether or not the participant is subsequently let down by the activity or pleasantly surprised.
- 6) Staff will measure the participant's interpupillary distance using sliding calipers.
- 7) Participants will be given 45 active minutes to engage with the intervention. Groups include:

Group 1 (VR): The VR group will receive a virtual reality simulation designed during Phase 1 of this study.

Group 2 (mock MRI): The mock MRI will be provided by the CLS, according to the current care plan which consists of exposing children to the mock MRI, medical devices, and procedures. The mock MRI is located within the BCCH medical imaging facility.

Group 3 (booklet): The standard MRI preparation booklet group will provide access to a series of printed photos and text showing the MRI experience step-by-step to help prepare for the MRI.

- 8) Participants will be asked to indicate on the Smileyometer how good they actually thought the activity was overall (1 minute).
- 9) Participants will be informed that they will now be completing a simulation test with the MRI scanner. Participants will be reminded of their free and informed ongoing consent.
- 10) The participant will be transferred to the simulation room, located in the medical imaging center at BCCH. Upon entering the simulation room, participants will verbally complete the VPT with staff (during test). In parallel, parents will complete the Short STAI on the iPad. (5 minutes)
- 11) Participants will be guided through a mock MRI and be assessed using MoTrack®, an objective head motion tracking system.³² The simulation will be completed over 20 minutes and will involve progression through the “MRI procedure”, remaining in the bore for 8 minutes. All participants will receive the same type of simulated scan. We will not be simulating any invasive procedures that can sometimes occur during the MRI (i.e. an IV or intravenous contrast liquid). Please note that this assessment involves a mock procedure using the simulator, not a real MRI.
- 12) Immediately following the simulation, participants will verbally complete the VPT with staff (post-test). In parallel, parents will complete the Short STAI on the iPad. (10 minutes).

- 13) Users will be asked to indicate on the *Smileyometer* how they thought the preparation activity was overall in preparing them for the MRI. Parents/guardians will be asked to complete the USE Questionnaire.
- 14) Staff will ask the user open-ended questions on the preparation materials according to three separate criteria of fun, ease of use, and how good it was for learning about the MRI experience. The final usability assessment will take a total of 10 minutes.
- 15) After the session is "complete", children will be told that they "happen to have some time left" so they can play with any of the preparation materials offered (VR, Mock MRI, Booklet) for 5-minutes if they want to "because they did so well during the activity." This will give children a natural choice selection and will be used to gauge preferences for the activities.
- 16) A verbal session debrief will include an opportunity for questions to mitigate any residual feelings of discomfort or anxiety that may arise from the project's activities.

Outcome Measures

The measures used to evaluate the intended outputs and outcomes associated with this project are outlined below (**Table 4**).

Table 4. Outputs and outcomes associated with the project.

Measure	Immediate Outputs	Intended Outcome
Primary		
MoTrak®	# of participants "prepared" to be scheduled for an effective MRI	
Improve access to MRI preparation for children who:
 
 - Live out of town - Would like to practice skills at home - Have mobility issues 
Improve non-sedation rates for MRI scans.

Venham Pictoral Test & Short STAI	# of participants with reduced anxiety # of parents with reduced anxiety	
Improve access to MRI preparation materials.
 
Improve behavioral compliance during medical procedures.

Secondary		
Smileyometer	# of participants who find the delivery mode fun and engaging to use	
Improve acceptability of preparation materials.
 
Improve satisfaction.

USE Questionnaire	# of parents who find the preparation materials useful	
Improve acceptability of preparation materials.
 
Improve satisfaction.

Natural Choice Selection	# of participants who select the booklet # of participants who select the mock MRI # of participants who select virtual reality # of participants who select none	Identify preference for engaging. Identify frequency of contact and time engaging.
Length of Stay	Minutes spent per segment	Improve hospital efficiency
Guided Survey	# of participants who find the booklet fun, easy to use, and good for learning about the MRI experience # of participants who find the mock MRI fun, easy of use, and good for learning about the MRI experience # of participants who find the virtual reality game fun, easy of use, and good for learning about the MRI experience	Improve utility of MRI preparation materials. Identify frequency of contact and time engaging.
Interpupillary Distance	Average interpupillary distance per age	Improve headset configuration.

Primary Measures

Predictive Success in Avoiding Sedation

The predictive success in avoiding sedation will be measured using Motrak® software assessment. MoTrak® uses a sensor attached to the participant's head to determine the position of the head in space relative to a transmitter located within the simulator. The sensor records angular rotations as well as positional displacements from an initially calibrated position. This information is displayed and logged by the program in real-time, allowing objective observation of head motion in an MRI simulator.³² The fail threshold is set at 3mm of movement in any of the positional displacements (x,y,z), which is in accordance with imaging protocols at the Hospital.

Child Anxiety: Venham Picture Test – 5 minutes

Anxiety assessment with children will be completed in pictorial form to better adapt to the cognitive and communicative abilities and styles of younger children. The Venham Picture Test has been well-validated in children for assessing procedural anxiety^{33,34}, and comprises eight cards which two figures on each card, one anxious character and one non-anxious character. The children will be asked to point at the figure they feel most like at that moment. All cards will be shown in their number order. If the child points at the anxious figure, a score of one is recorded and if the child points at the non-anxious character, they will be given a score of zero. Children will complete the at three timepoints (before, during, after the mock MRI).

Secondary Measures

Parental Anxiety: Short State-Trait Anxiety Inventory (Short STAI) – 5 minutes

Anxiety assessment with parents/guardians and children at baseline, after completing the intervention, and before the mock MRI. The Short STAI is a 6-item, adapted version of the well-validated Spielberger State-Trait Anxiety Inventory Scale.³⁵ It distinguishes between general proneness to anxious behavior rooted in the personality and anxiety connected to a current state, and has been validated for use in children.³⁵

Demographics and Relevant History

Demographic and possible confounding information (age, sex, prior experience with medical imaging, experience with virtual reality, type of mobile phone) will be obtained through a data collection form. Data will be de-identified using a participant identification number.

Length of Stay (LoS)

For the purposes of this evaluation, we will define total LoS as the duration, in minutes, from starting the *preparation* segment to completion of the simulated *assessment*. Inter-segment times will also be recorded. Preparation time will be capped at 45 minutes. Assessment time will be capped at 20 minutes. Start of preparation will be noted as time when study staff finish describing the intervention and indicate it is time to begin the active preparation. Time will stop when the participant is “discharged” from the MRI simulation, before the natural choice selection exercise and debriefing process begins. Time spent transitioning between activities or breaks required for reasons unrelated to the evaluation will not be counted towards overall LoS.

Interpupillary Distance

Interpupillary Distance will assume normal conditions and be measured objectively before preparation using Pryor's (1969) method³⁶ to ensure appropriate set up of the virtual reality device.

[figure not shown]

FIG. 1. Formula for interpupillary distance.

Usability Testing

The Smileyometer – 1 minute

The Smileyometer^{30,31} is an instrument used for measuring the opinions of technology in children, and has been validated in multiple studies assessing educational materials and software. The Smileyometer is based on the Visual Analogue Scale,³⁷ consisting of a 5-point Likert scale that uses pictorial representations. Participants are asked to point to the face they relate to.

Guided Survey – 10 minutes

The RA will ask the participant several open-ended questions on the preparation materials according to three separate criteria of fun, ease of use, and how good it was for learning about the MRI experience.

USE Questionnaire – 10 minutes

The USE Questionnaire²³ will be administered to the parents/guardians after the mock MRI only. This will allow participants to compare the VR application to the “effective MRI” experience. The USE Questionnaire is a 7-point Likert rating scale that has been well-validated to assess a program’s usefulness, ease-of-use, ease of learning, and satisfaction.

Analysis and Interpretation

A priori power analysis was calculated using G-Power.³⁸ A total sample size (N) of 93 was calculated to be needed across the 3 groups (31 per group), with a significance level of 95% ($\alpha=0.05$) and a power of 90% ($\beta=0.10$), allowing for a 10% drop out rate. An effect size of 0.2 was selected to reflect the research suggesting that CLS preparation can reduce sedation rates by 20%.

Descriptive analysis will be conducted on the demographics and relevant history data.

Differences in predictive success of the MRI simulation ranking scores (pass or fail) will be examined using a Repeated Measures ANOVA, within-between interaction for three timepoint measurements (before, during, after) of anxiety and delivery type (VR, mock MRI, booklet). In the case of an off-normal distribution, non-parametric tests may be used. Multivariate analysis will test for possible confounding effects (demographics and relevant history).

Survey data (USE questionnaire, Smileyometer) will be analyzed using means and standard deviations of all respondents for each category of the questionnaires. The proportions of the participants reporting high, medium, or low levels will also be calculated.

Study staff will document responses to the guided survey and read the recorded answers back to participants to verify accuracy and elicit possible further reflection. All of the qualitative data will be uploaded to NVivo by study staff. When complete, study staff will code the information to identify major themes, gaps, barriers within the existing approach and the team will devise recommendations for improving the preparation programs. The phases of this process include:

- Familiarizing yourself with the data

- Generating initial codes
- Searching for themes
- Reviewing themes
- Defining and naming the themes
- Triangulation with other findings and producing a report

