4.2 Objectives and Hypotheses

Phase 1: Design and Development of the Virtual Reality Experience

1. Work with an interdisciplinary team to collaboratively develop an engaging prototype (V1.0) that models the MRI environment and experience at BCCH.

Phase 2: Technology Evaluation and Comparative Assessment

2. Evaluate the effectiveness in pre-procedural preparation through a comparative assessment against other modes of delivery currently offered at BCCH – including pre-procedural instructional booklet, and mock MRI with CLS.
 - a. *Hypothesis:* There will be differences in outcomes between the virtual reality group and the booklet group.
 - b. *Hypothesis:* There will be no difference in outcomes between the mock MRI and virtual reality simulation groups.
 - c. *Hypothesis:* Children will prefer the virtual reality and simulation exercises to booklet preparation.

Phase 3: Economic Evaluation and Impact Modeling

3. Evaluate costs and benefits of the VR solution and status quo; and conduct economic modelling on the prospective impact of operational integration.

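### Children are randomised only among the arms open when they can attend, and the plan neither lists nor analyses that open-arm set, so VR versus mock MRI is open to confounding by availability

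*Combined protocol and SAP*

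**What the plan says.** Section 4.4 (Protocol for Evaluating the Virtual Reality MRI Simulator) is open about the limit on allocation: "Given the restricted availability of the simulator, child life specialists, and the availability of participants", it says, "we are unable to fully randomly allocate participants". Instead, "participants will be randomly assigned to the intervention options available according to their individual availability". The example given is that "if a participant is available on a Thursday that virtual reality and booklet are available, they will be randomly allocated to one of these interventions". Mock MRI is not among the options on that day.

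The table of comparison groups in the same section gives a research assistant as facilitator for VR and booklet, and a child life specialist for mock MRI only.

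On data, the plan says: "The predictive variables (demographics and relevant history, and delivery type) will be captured at the start of the session". Under Demographics and Relevant History, the possible confounders are "age, sex, prior experience with medical imaging, experience with virtual reality, type of mobile phone". Under Analysis and Interpretation, the main model has time and delivery type, and a multivariate analysis is added for the demographic and history variables. The open-arm set, weekday and session date are not mentioned in any of these places.

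Section 4.2, hypothesis b, reads: "There will be no difference in outcomes between the mock MRI and virtual reality simulation groups".

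**The concern.** Under this rule, chance decides the arm within each set of open arms, but not across sets. A child who can come only when the specialist is away can be drawn into VR or booklet and never into mock MRI. The pooled VR arm then mixes restricted and unrestricted children, while the mock MRI arm holds only children who had mock MRI open.

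If the two kinds of children differ in how likely they are to pass, the VR versus mock MRI difference combines the effect of preparation with the effect of who could attend when. Hypothesis b is a claim of no difference, so such a mixture could hide a real difference or create a false one. The planned covariate analysis includes age, but it removes only the part of an availability effect that runs through the listed variables. Pass/fail, the primary outcome, has no baseline value to adjust for. If the open-arm set is not kept, the contrast cannot later be restricted to children who could have entered either arm.

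Two comparisons are less exposed. In the plan's example, VR versus booklet is not biased, because both arms draw on the same children. For anxiety, the group-by-time interaction is affected only if availability predicts change in anxiety; a constant difference between availability groups drops out.

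**Working it through.** **Inputs from the documents.** A minimum of 93 children, 31 per group (Section 4.4); the allocation rule and its example; pass/fail as the primary outcome.

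**Assumptions, because the documents give no figures.** A share *s* of children has only VR and booklet open, and the rest have all three arms open. Chances are equal among open arms. There is no true effect and no covariate adjustment. The pass rates of restricted and unrestricted children differ by *g*.

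**Step 1: make-up of the arms.** The probability of entering VR is s/2 for restricted children plus (1−s)/3 for the others. The restricted share of the VR arm is therefore 0.5s / (0.5s + (1−s)/3). In mock MRI it is 0. At s = 0.3: 0.15 / (0.15 + 0.2333) = 0.391.

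**Step 2: bias.** Crude bias in VR minus mock MRI = g × restricted share of VR. At s = 0.3 and g = 20 points: 20 × 0.391 = 7.8 points.

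**Step 3: arm size.** If allocation stops at 93, the expected mock MRI arm is 93(1−s)/3. At s = 0 this returns the planned 31. The total for an expected 31 in mock MRI, with allocation continuing among open arms, is 93/(1−s).

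**Step 4: precision of the restricted comparison.** Among children with both arms open, each arm has 31(1−s) children. At an assumed 75% pass rate the 95% half-width is 1.96 × √(2 × 0.75 × 0.25 / (31(1−s))).

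| s | Restricted share of VR | Bias, g = 10 | Bias, g = 20 | Mock MRI n at 93 | Total for 31 in mock MRI | Half-width, both open |
|---|---|---|---|---|---|---|
| 0 | 0 | 0 | 0 | 31 | 93 | 21.6 |
| 10% | 14.3% | 1.4 | 2.9 | 27.9 | 103.3 | 22.7 |
| 20% | 27.3% | 2.7 | 5.5 | 24.8 | 116.2 | 24.1 |
| 30% | 39.1% | 3.9 | 7.8 | 21.7 | 132.9 | 25.8 |
| 50% | 60.0% | 6.0 | 12.0 | 15.5 | 186.0 | 30.5 |
| 70% | 77.8% | 7.8 | 15.6 | 9.3 | 310.0 | 39.4 |

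Bias and half-width are in percentage points. The bias favours VR if restricted children pass more often, and mock MRI if they pass less often. With g = 0 there is none.

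**Step 5: simulation.** In 20,000 trials of 93 children (restricted versus unrestricted pass rates 65/85, 85/65 and 75/85), the crude bias agreed with the formula within 0.2 points. The mean bias was within 0.2 points of zero both among both-open children and for VR versus booklet.

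A separate run of 4,000 trials took an 82% pass rate in unrestricted children, gaps of 10 to 30 points and s of 20 to 50%. The type I error of the pooled 5% test for VR versus mock MRI was 5.6% to 23.6%. Restricting to both-open children brought it to 3.9% to 5.6%.

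**The case against.** The strongest reply is that nothing in the documents suggests that availability predicts head movement. The plan discloses the limitation and intends a covariate analysis, and the bias figures above leave that analysis out. This is right as far as it goes: the figures describe the crude contrast, the adjusted bias could be smaller, and neither the share nor the gap has a source. But disclosure does not deal with the problem in the analysis, and the plan lists nothing that would show whether the assumption of no availability effect is safe.

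It can also be said that the data form is not the allocation log. Staff must know the open arms to run the randomiser and may well keep them. So the supported statement is that no section says the set is recorded or used. Figures 2 and 3 could not be read, so this rests on the written text. Partial checks also exist: arms can be compared on the listed covariates and on pre-test child and parent anxiety, which are measured before the arm is revealed. These checks cannot exclude residual confounding.

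The arm-size projections assume that allocation continues among all open arms. If each arm instead closes at 31, the projections change, but the bias at a 20-point gap barely moves: 2.9, 5.5, 7.9, 12.1 and 15.6 points.

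The 75% pass rate is a choice. With the 82% conversion rate in Section 3.0 (283/344, a different population), the half-widths become about 20, 21, 23, 27 and 35 points, against 19 with 31 per arm.

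Finally, restriction trades bias for variance. At s = 0.3 and a 10-point gap, taking 75% for the variance, the crude contrast has root-mean-square error √(0.1875/35.65 + 0.1875/21.7 + 0.039²) = 12.4 points, against √(0.375/21.7) = 13.1 for the restricted one. At a 20-point gap, restriction has the lower error from s = 20% upward. That trade-off is real. It does not defeat the case for restriction, which analyses the children by the sets within which they were randomised.

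**Conclusion.** The concern holds. The structural point is certain from the text: randomisation operates within open-arm sets, the plan's own example closes mock MRI, and no listed variable or model term carries the set. The pooled VR versus mock MRI contrast for hypothesis b is therefore open to confounding by availability. Whether it is actually biased is not known. Under the stated assumptions the crude bias runs from 1.4 to 7.8 points for a 10-point gap and from 2.9 to 15.6 points for a 20-point gap, as the restricted share goes from 10% to 70%. VR versus booklet is unaffected in the plan's example, although the plan does not guarantee that those two arms are always open together. This should be fixed: it is cheap to do at allocation and may be impossible to repair afterwards.

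**What to change.** - Record the set of open arms at each allocation, as data.
- Define VR versus mock MRI as a comparison among children for whom both arms were open, and VR versus booklet likewise. Stratify by or adjust for open-arm set, with age as a prespecified covariate. Apply the same restriction to the anxiety analysis.
- Leave any child with only one open arm out of the randomised contrasts and report that child descriptively.
- Report how many children had each open-arm set.
- State whether arms close at 31 or allocation continues among open arms.

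The practical cost is one field on the allocation log and a restricted, stratified analysis. The statistical cost is a smaller VR versus mock MRI comparison: at a 75% pass rate and 93 children, the half-width is about 23, 24, 26, 31 and 39 points for restricted shares of 10, 20, 30, 50 and 70%, against 22 with 31 per arm. Restoring 31 in mock MRI means recruiting beyond 93, which the plan permits because it states 93 as a minimum.

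### The allocation rule is not designed to deliver the stated 31 per group; mock MRI is the arm most likely to fall short, by an amount that depends on an availability the plan does not state

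*Combined protocol and SAP*

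**What the plan says.** All the relevant text is in section 4.4 (Phase 2).

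- Target: "A minimum of 93 participants (31 participants per group) aged 4-to-13 will be recruited through convenience sampling".
- Allocation: "Given the restricted availability of the simulator, child life specialists, and the availability of participants, we are unable to fully randomly allocate participants". The rule that follows is that "participants will be randomly assigned to the intervention options available according to their individual availability". The illustration is a day on which VR and booklet are on offer and mock MRI is not.
- Staffing: in the table of comparison groups, a child life specialist facilitates mock MRI and a research assistant facilitates the other two arms.
- Assessment: the implementation steps take every child, whatever the arm, through the same simulator test.
- Sample size, under Analysis and Interpretation: "A total sample size (N) of 93 was calculated to be needed across the 3 groups (31 per group"), at 90% power and "allowing for a 10% drop out rate". The analysis named is a "Repeated Measures ANOVA, within-between interaction for three timepoint measurements (before, during, after) of anxiety and delivery type".

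Hypothesis 2b in section 4.2 expects no difference between mock MRI and VR. The plan gives no margin, precision or power for that comparison.

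**The concern.** The target implies three equal groups, but the rule makes each group's size depend on how often its arm is open. An arm that is open to fewer children gets fewer children, and nothing in the plan corrects for this.

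The likely short arm is mock MRI. The reason is the child life specialist, whom only that arm needs. Scarcity of the simulator does not by itself single it out, because all three arms need the simulator for the assessment.

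Mock MRI is one side of hypothesis 2b. A thin arm widens the interval for VR minus mock MRI. Where the hypothesis is no difference, an imprecise comparison is more likely to show none, and that result then says little.

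There is also a question of which children provide the randomised contrast. A VR child seen when mock MRI was closed could not have drawn mock MRI, so only children for whom both were open give a randomised comparison of the two.

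**Working it through.** **The plan's own figure.** I took the effect size as Cohen's f = 0.2, alpha 0.05, power 0.90, three groups, the within-between interaction, and G*Power's usual noncentrality f²·N·m/(1 − ρ).

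- Three timepoints with ρ = 0.5 give N = 67, and 67/0.9 = 74.4, so 75.
- Two measurements with ρ = 0.5 give 83, and 83/0.9 = 92.2, so 93.
- Three timepoints with ρ = 0.37 give 84, and 84/0.9 = 93.3.

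So 93 can be reached, but the stated inputs do not fix it, because the correlation is not given. What follows takes 93 and 31 per group as they stand.

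**Assumptions for the allocation.** The documents give neither the draw probabilities nor the share a of children for whom mock MRI is open. I assume equal chance among open arms, VR and booklet always open, and exactly 93 enrolled, and I show a range for a.

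**Formulas.**

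- Expected mock MRI n = 93 × a/3. Each other arm = (93 − mock n)/2.
- SE ratio, whole groups = √[(1/n_mock + 1/n_VR)/(2/31)].
- SE ratio, children with both arms open: n = 93a/3 in each arm, so the ratio is 1/√a.
- Enrolment needed for an expected 31 in mock MRI = 93/a.
- Chance that mock MRI reaches 31: binomial, 93 draws, probability a/3.

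| a | Mock MRI n | VR and booklet n, each | SE ratio, whole groups | SE ratio, both open | Chance of 31 or more | Enrolment for 31 |
|---|---|---|---|---|---|---|
| 1 | 31 | 31 | 1.00 | 1.00 | 0.54 | 93 |
| 0.9 | 27.9 | 32.6 | 1.02 | 1.05 | 0.27 | 103 |
| 0.75 | 23.3 | 34.9 | 1.05 | 1.15 | 0.04 | 124 |
| 0.5 | 15.5 | 38.8 | 1.18 | 1.41 | below 0.001 | 186 |
| 1/3 | 10.3 | 41.3 | 1.37 | 1.73 | below 0.001 | 279 |

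Example at a = 0.5: mock n = 93 × 0.5/3 = 15.5 and VR n = (93 − 15.5)/2 = 38.75. The whole-group ratio is √[(0.0645 + 0.0258)/0.0645] = √1.4 = 1.18.

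**In percentage points.** For illustration, use a pass rate of 283/344 = 82% in both arms, from the hospital's simulation statistics in section 3.0 (conversion to non-sedated MRI, not a MoTrak pass rate). The 95% half-width at 31 v 31 is 1.96 × √(0.823 × 0.177 × 2/31) = 19.0 points. With whole groups it becomes 19.3, 20.0, 22.5 and 26.0 points at a = 0.9, 0.75, 0.5 and 1/3. With both-open children only it becomes 20.0, 22.0, 26.9 and 32.9. The normal approximation is rough at the smallest sizes.

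**If full arms close at 31 instead.** VR and booklet fill, on average, after 31/[a/3 + (1 − a)/2] children. At a = 0.75 that is 82.7 children, of whom 82.7 × 0.25 = 20.7 are in mock MRI, so about 10 of its 31 places are then filled without a draw. At a = 0.5 it is 74.4 children and 12.4 in mock MRI, leaving about 19 of 31.

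**Blocking alone.** With all arms always open (a = 1), 400,000 simulated unblocked allocations of 93 gave a mean SE ratio of 1.01 and a 95th percentile of 1.08. A single arm's size ranged from 22 to 40 (95% range).

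**The case against.** The strongest reply is that the target is a minimum. Recruitment may continue past 93, or full arms may close, until every arm has 31. That stands: a reader might infer that the rule makes 31 per group impossible, and the documents do not support this. What they lack is a rule saying which route will be taken. Each has a cost: about 93/a children, in a study whose own recruitment text reports low enrolment, or a final run of children placed in mock MRI without randomisation.

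The size of the shortfall is also unknown. No availability share is given, the example day carries no frequency, and equal chance is my reading of an unweighted draw. If VR or booklet is sometimes closed while mock MRI is open, mock MRI's share rises. At a = 0.9 the whole-group loss is only 2% in SE.

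A reader might further infer that the VR–mock MRI comparison is much less precise than the plan claims. The plan claims no precision for it. The stated power is for an overall interaction, so the only yardstick is what 31 v 31 implies. The larger ratios apply only if the comparison is restricted to children with both arms open, whereas the planned analysis compares whole groups. The case for the restriction is that only those children were randomised between the two arms.

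Finally, the absence of blocking is a minor matter on its own, costing about 1% in SE on average.

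**Conclusion.** The point holds in a limited form, as a should-fix. The stated group size is not what the stated rule is built to produce. Under equal-chance draws, with VR and booklet always open and 93 enrolled, the expected mock MRI group is below 31 for every availability share below 1. The loss of precision against 31 v 31 is slight if mock MRI is open to nine children in ten. If it is open to half, the loss is material: SE up 18% with whole groups and 41% among children who could have drawn either arm. The documents do not show where in this range the study lies. That mock MRI is the short arm is an inference from its staffing and from the plan's example, not something the plan states.

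**What to change.** 1. State the allocation ratio and the anticipated share of children for whom mock MRI will be open.
2. Prepare permuted-block lists in advance, one for each set of open arms, and record each child's set at allocation.
3. Book families onto days with all three arms open whenever they can attend one. This raises a directly and does more for the comparison than blocking.
4. Replace 31 per group with the expected number per arm and per comparison at the anticipated availability. At a = 0.75 and 93 enrolled, under the assumptions above, this would read about 23 in mock MRI and 35 in each other arm, with VR versus mock MRI resting on about 23 v 23.
5. Say in the analysis section that the randomised VR–mock MRI comparison rests on children for whom both arms were open.
6. If 31 in every arm is still wanted, write down how it will be reached and what that implies for total enrolment or for unrandomised places.

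The cost is a less favourable stated size and some scheduling and list preparation. The allocation has to be settled before enrolment, because it cannot be repaired afterwards.
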